5.6.3.2. Procedures and Guidance for Enterocolitis

Subjects should be carefully monitored for signs and symptoms of enterocolitis (such as diarrhea, abdominal pain, mucus or blood in stool, with or without fever) and of bowel perforation (such as sepsis, peritoneal signs, and ileus). In symptomatic subjects, rule out infectious etiologies and consider endoscopic evaluation for persistent or severe symptoms.

Subjects should be thoroughly evaluated to rule out any alternative etiology (eg, disease progression, other medications, infections including testing for clostridium difficile toxin, etc). Steroids should be considered in the absence of clear alternative etiology, even for low grade events, in order to prevent potential progression to higher grade event. Use analgesics carefully; they can mask symptoms of perforation and peritonitis. The recommended approach for handling enterocolitis is detailed in [Table 11](#).

Table 11: Recommended Approach for Handling Enterocolitis

Toxicity Grade	Withhold/Discontinue Durvalumab and Epacadostat	Guidance for Restarting Study Treatment	Supportive Care
Grade 1	No action.	Not applicable.	
 • Closely monitor for worsening symptoms. • Consider symptomatic treatment, including hydration, electrolyte replacement, dietary changes (eg, American Dietetic Association colitis diet), and loperamide. Use of probiotics as per treating physician's clinical judgment.
Grade 2	Withhold durvalumab and epacadostat.	
Hold treatment until resolution to \leq Grade 1 or baseline.
 
 • If toxicity improves to \leq Grade 1, then study treatment can be resumed after completion of steroid taper. Epacadostat will be reduced by 1 dose level, and durvalumab will resume at the same dose/schedule. • If toxicity worsens, treat as Grade 3 or Grade 4. 	
 • Consider symptomatic treatment, including hydration, electrolyte replacement, dietary changes (eg, American Dietetic Association colitis diet), and loperamide and/or budesonide. • Promptly start prednisone 1-2 mg/kg per day PO or IV equivalent. • If event is not responsive within 3-5 days or worsens despite prednisone 1-2 mg/kg per day PO or IV equivalent, GI consult should be obtained for consideration of further work-up such as imaging and/or colonoscopy to confirm colitis and rule out perforation, and prompt treatment with IV methylprednisolone 2-4 mg/kg per day started. • If still no improvement within 3-5 days despite 2-4 mg/kg IV methylprednisolone, promptly start immunosuppressives such as infliximab at 5 mg/kg once every 2 weeks. 
Caution: Important to rule out bowel perforation and refer to infliximab label for general guidance before using infliximab.
 
 • Consult with medical monitor if no resolution to \leq Grade 1 in 3-4 days. • Once improving, gradually taper steroids over \geq 28 days and consider prophylactic antibiotics, antifungals, and anti-PCP treatment (refer to current NCCN Guidelines for treatment of cancer-related infections [Category 2B recommendation]).

Table 11: Recommended Approach for Handling Enterocolitis (Continued)

Toxicity Grade	Withhold/Discontinue Durvalumab and Epacadostat	Guidance for Restarting Study Treatment	Supportive Care
Grade 3 and Grade 4	Discontinue epacadostat and durvalumab.	Not applicable.	
 • Treatment with systemic corticosteroids (IV administration) should be initiated promptly at a dose of 2-4 mg/kg per day of prednisone or equivalent. • Monitor stool frequency and volume and maintain hydration. • Urgent GI consult and imaging and/or colonoscopy as appropriate. • If still no improvement within 3-5 days of IV methylprednisolone 2-4 mg/kg per day or equivalent, promptly start further immunosuppressives (eg, infliximab at 5 mg/kg once every 2 weeks). Caution: Ensure GI consult to rule out bowel perforation and refer to infliximab label for general guidance before using infliximab. • Once improving, gradually taper steroids over ≥ 28 days and consider prophylactic antibiotics, antifungals, and anti-PCP treatment (refer to current NCCN Guidelines for treatment of cancer-related infections [Category 2B recommendation]).

5.6.3.3. Procedures and Guidance for Hepatitis

Monitor LFTs (hepatic transaminase, alkaline phosphatase, and bilirubin levels) and assess subjects for signs and symptoms of hepatotoxicity on Day 1 of each cycle before dosing of durvalumab. In subjects with hepatotoxicity, rule out infectious or malignant causes and increase frequency of LFT monitoring to twice per week until resolution. Recommendations for management of hepatitis are shown in [Table 12](#).

Table 12: Recommended Approach for Handling Hepatitis

Toxicity Grade	Withhold/Discontinue Epacadostat and Durvalumab	Guidance for Restarting Study Treatment	Supportive Care
Grade 1	No dose modifications. If it worsens, then treat as Grade 2 event.	Not applicable.	Increase frequency of LFT monitoring to twice per week until LFTs return to baseline.
Grade 2 elevation in AST/ALT or total bilirubin	Withhold epacadostat and durvalumab.	
Hold treatment until resolution to \leq Grade 1 or baseline.
 
 • If improves to \leq Grade 1 or baseline, resume study treatment after completion of steroid taper. Epacadostat will be reduced by 1 dose level, and durvalumab will resume at the same dose/schedule. • If toxicity worsens, then treat as Grade 3 or Grade 4. 	
 • Regular and frequent checking of liver chemistries (eg, every 1-2 days) until improving or resolved. • Rule out viral and other etiologies. • If event is persistent ($>$ 3-5 days) or worsens, promptly start prednisone 1-2 mg/kg per day PO or IV equivalent. • If still no improvement within 3-5 days despite prednisone 1-2 mg/kg per day PO or IV equivalent, consider additional work-up and start prompt treatment with IV methylprednisolone 2-4 mg/kg per day. • If still no improvement within 3-5 days despite 1-4 mg/kg per day methylprednisolone IV or equivalent, promptly start immunosuppressives (mycophenolate mofetil). Discuss with medical monitor if mycophenolate mofetil is not available. Infliximab should NOT be used. • Once improving, gradually taper steroids over \geq 28 days and consider prophylactic antibiotics, antifungals, and anti-PCP treatment (refer to current NCCN Guidelines for treatment of cancer-related infections [Category 2B recommendation]).

Table 12: Recommended Approach for Handling Hepatitis (Continued)

Toxicity Grade	Withhold/Discontinue Epacadostat and Durvalumab	Guidance for Restarting Study Treatment	Supportive Care
Grade 3 elevation in AST/ALT of $> 5 \times \text{ULN}$ but $< 8 \times \text{ULN}$ OR Grade 3 elevation in total bilirubin of $\leq 5 \times \text{ULN}$	Withhold epacadostat and durvalumab.	Hold treatment until resolution to \leq Grade 1 or baseline. 
 • Resume study treatment if elevations downgrade \leq Grade 1 or baseline within 14 days; epacadostat will be reduced by 1 dose level, and durvalumab will resume at the same dose/schedule. • If AE does not resolve to \leq Grade 1 or baseline within 14 days: Discontinue study treatment (exceptions may be made by the medical monitor on a case by case basis). • Permanently discontinue study treatment for any case meeting Hy's law criteria (AST and/or ALT $> 3 \times \text{ULN}$ + bilirubin $> 2 \times \text{ULN}$ without initial findings of cholestasis (ie, elevated alkaline P04) and in the absence of any alternative cause. 	
 • Promptly initiate empiric IV methylprednisolone 1-4 mg/kg per day or equivalent • If still no improvement within 3-5 days despite IV methylprednisolone 1-4 mg/kg per day or equivalent, promptly start treatment with immunosuppressive therapy (mycophenolate mofetil). Discuss with medical monitor if mycophenolate is not available. Infliximab should NOT be used. • Hepatology consult, abdominal work-up, and imaging, as appropriate. • Once improving, gradually taper steroids over ≥ 28 days and consider prophylactic antibiotics, antifungals, and anti-PCP treatment (refer to current NCCN Guidelines for treatment of cancer-related infections [Category 2B recommendation]).
Elevation in AST/ALT of $> 8 \times \text{ULN}$ OR Elevation of total bilirubin of $> 5 \times \text{ULN}$	Discontinue epacadostat and durvalumab.	Not applicable.	

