5.6.3.12. Procedures for Immune-Related Adverse Events Not Specifically Described Above

Table 20 provides information on the diagnosis and treatment of potential irAEs.

Table 20: General Guidance for Diagnosis and Treatment of Immune-Related Adverse Events (Not Described in Previous Sections)

Subject evaluation to identify any alternative etiology
In the absence of a clear alternative etiology, all events of inflammatory nature should be considered to be immune-related
Symptomatic and topical therapy should be considered for low-grade events
Systemic corticosteroids should be considered for a persistent low-grade event or for a severe event
More potent immunosuppressives should be considered for events not responding to systemic steroids

In general, both study drugs should be permanently discontinued for clinically significant or severe irAEs or for events where the steroid course cannot be tapered below 10 mg/day prednisone equivalent to manage symptoms. Following an irAE where treatment was withheld, study treatment may resume when the following conditions are met: steroid taper has reached \leq 10 mg/day prednisone or equivalent, symptoms have improved to \leq Grade 1 within 4 weeks of

onset (or longer with medical monitor approval), and, as appropriate, physiologic replacement of hormones has been instituted. Additional treatment regarding modifications to study drug administration for irAEs is detailed in [Table 21](#).

Table 21: Recommended Approach for Handling Immune-Related Adverse Events (Not Described in Previous Sections)

Toxicity Grade	Withhold/Discontinue Epacadostat and Durvalumab	Guidance for Restarting Study Treatment
Grade 1	No action.	Not applicable.

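### Table 12 sets no steroid condition for restarting treatment after Grade 3 hepatitis, although the milder Grade 2 row requires the steroid taper to be finished first

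*Protocol*

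**What the plan says.** Protocol Section 5.6.3.3, Table 12, handles immune-related hepatitis by grade.

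- **Grade 2.** Both drugs are held. Prednisone starts only if the event persists beyond 3-5 days or worsens, and is tapered over at least 28 days once the event improves. When values reach Grade 1 or baseline, the subject may "resume study treatment after completion of steroid taper", with epacadostat one level lower. The row also says: "If toxicity worsens, then treat as Grade 3 or Grade 4".
- **Grade 3** (AST/ALT above 5 and below 8 × ULN, or bilirubin up to 5 × ULN). Both drugs are held. Supportive care is "Promptly initiate empiric IV methylprednisolone 1-4 mg/kg per day or equivalent", with no trigger attached, and then "Once improving, gradually taper steroids over ≥ 28 days". The restart cell reads "Resume study treatment if elevations downgrade" to at most "Grade 1 or baseline within 14 days; epacadostat will be reduced by 1 dose level, and durvalumab will resume at the same dose/schedule". If the event has not resolved in 14 days, treatment stops unless the medical monitor makes an exception. Cases meeting Hy's law stop permanently.
- **Higher values.** Both drugs are discontinued.

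The Grade 3 restart cell mentions neither completion of the taper nor a steroid dose.

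**The concern.** The two rows are in the wrong order of caution on this one point. The milder event, which may never need steroids, must wait out any taper. The more severe event, for which steroids are recommended from the outset, may restart on its liver values alone. A subject who crosses from Grade 2 to Grade 3 loses the taper condition by getting worse.

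Liver values that normalise under steroids do not show that the event stays resolved without them. Restarting both drugs mid-taper re-exposes the subject before that is known. Protocol Section 1.3.3 itself warns that the combination may cause more frequent or more severe immune toxicity than either drug alone. The medical monitor must rule on each restart with two rows that point in different directions and no stated steroid level for Grade 3.

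**Working it through.** The plan gives no figure to reproduce. The check is a count of days from Table 12, then a search for a steroid condition elsewhere.

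**Inputs from Table 12**

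- Grade 3 resolution limit: 14 days. The table does not say when this clock starts. I take Day 0 as event onset.
- Minimum taper at either grade: 28 days, starting once the event improves.
- Grade 2 steroid start when triggered by persistence: after about 3-5 days.

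**Grade 3: taper left if restart coincides with resolution**

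Let improvement, and so the taper, begin on Day d ≥ 0, and resolution fall on Day r ≤ 14. The taper ends no earlier than Day d + 28.

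- Taper left = d + 28 − r.
- The smallest value is at d = 0, r = 14: 0 + 28 − 14 = **14 days**, half of the minimum taper.
- Later improvement or earlier resolution leaves more. For example, d = 3 to 5 (assumed) with r = 14 leaves 17 to 19 days.
- At the minimum, 14 days of twice-daily dosing is 14 × 2 = 28 epacadostat doses. The 14-day durvalumab schedule adds at least one infusion.

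**Grade 2 treated with steroids: earliest restart**

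- Persistence trigger, improvement on the day steroids start: 3 + 28 = Day 31 to 5 + 28 = Day 33.
- Steroids on Day 0 because the event worsens: 0 + 28 = Day 28.
- Compared with a Grade 3 restart by Day 14, the milder grade waits at least 28 − 14 = 14 days longer, or 31 − 14 = 17 days longer under the persistence trigger.

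**Is the condition supplied elsewhere in the Protocol?**

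| Section | What it requires | Steroid criterion for a Grade 3 hepatitis restart? |
|---|---|---|
| 5.6.2 | Monitor discussion before resuming after an interruption for liver test abnormalities | No |
| 5.6.3 | Immediate monitor discussion of immune-related events of Grade 2 or higher | No |
| 5.10.2 | Monitor approval for steroids at or above 10 mg/day to treat immune-related toxicity | No, it governs steroid use and not restart |
| 5.6.3.3 | In hepatotoxicity, "increase frequency of LFT monitoring to twice per week until resolution" | No |
| 7.3.6.1.1 | Once steroids begin, liver tests at the institutional interval or about weekly, whichever is shorter | No |
| 5.6.3.12 | Restart after a withheld immune-related event once the taper is at 10 mg/day prednisone or less | Yes, but its scope is doubtful |

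Section 5.6.3.12 is headed "Procedures for Immune-Related Adverse Events Not Specifically Described Above". Section 5.6.3 likewise describes it as the general guidance for events not detailed elsewhere, and hepatitis has its own section. The more natural reading is that its threshold does not govern Table 12.

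**The case against.** The strongest reply is that the threshold in Section 5.6.3.12 already applies. Its sentence is worded for any immune-related event after which treatment was withheld. Table 21 in that section also refers to endocrinopathies and myocarditis, which have tables of their own. A monitor could reasonably apply 10 mg/day where the hepatitis cell is silent. This stands as a real ambiguity. It does not remove the need for an edit: the heading points the other way, and even on the broad reading the Grade 2 row would still ask for more than the Grade 3 row.

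Second, a reader might infer that the protocol directs a mid-taper restart at Day 14. It does not. The 14 days is a limit on resolution, the cell gives no restart date, and every restart after a liver hold must first be discussed with the monitor. The defect is that the cell permits an early restart without a criterion.

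Third, it is tempting to say that every Grade 3 case receives steroids. Table 12 is titled as a recommended approach, and Section 5.6.3.3 first asks that infectious and malignant causes be ruled out. The day count holds for subjects treated as the table recommends.

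Fourth, a reader might infer that all such subjects would still be above 10 mg/day at restart. The protocol gives no taper shape, so the documents cannot show that.

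Finally, taper completion is not a uniform rule here. Table 19 (myositis) restarts at both Grade 2 and Grade 3 on resolution, with no taper condition. Amendment 7 revised the toxicity guidance to align with durvalumab guidelines that are not among the documents, so intent cannot be settled. This weakens any claim that full completion must be the right rule. It does not explain why only the milder hepatitis row carries the condition.

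**Conclusion.** The point holds as a minor safety correction. Table 12 states a steroid condition for restart at Grade 2 and none at Grade 3, and no other section clearly supplies one. For a subject treated as recommended who restarts on resolution, at least 14 days of taper remain. That figure assumes the minimum 28-day taper, a 14-day clock running from onset, and restart on the day of resolution.

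The required monitor discussion, the exclusion of values above the row's cut-offs and the Hy's law stop all reduce the risk. Few subjects are likely to be affected: the Amendment 4 rationale in Appendix E (January 2016) reports a low incidence of Grade 3 or greater ALT and AST elevations up to that time. The analysis of objective response is not touched.

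**What to change.** In the Table 12 Grade 3 restart cell, add that treatment resumes only once the steroid taper has reached 10 mg/day prednisone equivalent or less. This is the protocol's own threshold from Section 5.6.3.12, so it introduces no new standard. If the sponsor prefers to match the Grade 2 row, require completion of the taper instead. In either case, state that the 14 days limits the time to resolution and not the date of restart.

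The edit is one phrase and one clarifying sentence, subject to the usual sponsor and IRB/IEC approval of protocol changes. The cost is a later restart. With taper completion, the earliest restart is 0 + 28 = Day 28, and later whenever improvement begins later. Many restarts would then fall at or beyond 4 weeks, where Section 5.7.1 calls for monitor approval, and some subjects might not resume. The 10 mg/day option can allow an earlier restart, by an amount that depends on the taper used, which the protocol does not specify.

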5.7. Withdrawal of Subjects From Study Treatment

5.7.1. Withdrawal Criteria

Subjects **must** be withdrawn from study treatment for the following reasons:

- The subject completes 12 months of study treatment with epacadostat and durvalumab, or had completed 12 months of combination treatment (prior to Amendment 6 [28 JUN 2017]), and has taken epacadostat monotherapy for an additional 12 months (for a total of 24 months of study treatment).
 - Note: A subject may be granted an exception by the medical monitor to continue on epacadostat monotherapy beyond 24 months of overall treatment duration if they are clinically stable or clinically improved. Approvals to remain on epacadostat monotherapy will require continuing review every 3 months.
- In the investigator's medical judgment, further participation would be injurious to the subject's health or well-being.
- The subject becomes pregnant.
- Consent is withdrawn by subject or legal representative (such as legal guardian).
- The subject has experienced an unacceptable toxicity as described in Section 5.6 or a toxicity that does not recover in 4 weeks. Investigators who wish to continue treatment after a treatment delay of 4 weeks should consult with the sponsor's medical monitor for approval.
- Confirmed radiographic progression of disease per modified RECIST v1.1. See Section 7.4 for details on subjects with unconfirmed radiographic progression. An exception to continue on treatment with confirmed radiographic progression may be granted to clinically stable subjects. See Section 7.4 for additional details.
- The study is terminated by the sponsor.
- The study is terminated by the local health authority or IRB or IEC.
- \geq Grade 3 infusion reaction.
- Initiation of alternative anticancer therapy including another investigational agent.

A subject **may** be withdrawn from the study treatment as follows:

- If subject attains a CR (see Section 7.4.3), and the decision is made to discontinue durvalumab.
- If, during the course of the study, a subject is found not to have met eligibility criteria, the medical monitor, in collaboration with the investigator, will determine whether the subject should be withdrawn from study treatment. See Section 11.3, Protocol Adherence.
- If a subject is noncompliant with study procedures or study drug administration in the opinion of the investigator, the sponsor should be consulted for instruction on handling the subject.

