8.2.2. Potential Drug-Induced Liver Injury (or Hy's Law)

Wherever possible, timely confirmation of initial liver-related laboratory abnormalities should occur prior to the reporting of a potential DILI event (also known as Hy's Law). All occurrences of potential DILIs, meeting the defined criteria, must be reported as SAEs (see Section 8.3.2 for reporting details).

Potential drug induced liver injury is defined as:

1. AT (ALT or AST) elevation > 3 times ULN
AND
2. Total bilirubin > 2 times ULN, without initial findings of cholestasis (elevated serum alkaline phosphatase),
AND
3. No other immediately apparent possible causes of AT elevation and hyperbilirubinemia, including, but not limited to, viral hepatitis, pre-existing chronic or acute liver disease, or the administration of other drug(s) known to be hepatotoxic.

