8.3.2. Reporting

To ensure subject safety, every SAE, regardless of suspected causality, occurring after the subject has signed the ICF and up to the last study visit, or up to 90 days after the last dose of study treatment, must be reported to the sponsor (or designee) within 24 hours of learning of its occurrence. Any SAEs experienced after this period should be reported to the sponsor (or designee) only if the investigator suspects a causal relationship to the study drug. Recurrent episodes, complications, or progression of the initial SAE must be reported as the follow-up to the original episode within 24 hours of the investigator receiving the follow-up information. An SAE occurring at a different time interval or otherwise considered completely unrelated to a previously reported one should be reported separately as a new event. Previously planned (before providing informed consent) surgeries should not be reported as SAEs unless the underlying medical condition worsens over the course of the study.

Information about all SAEs is collected and recorded on the Serious Adverse Event Report Form. The investigator must assess and record the relationship of each SAE to each specific study drug (if there is more than 1), complete the SAE Report Form in English, and send the completed, signed form by fax within 24 hours to the sponsor or its designee. The investigator must assess if there is a reasonable possibility that the SAE is related to the study treatment: unrelated (no) or related (yes).

Serious AEs related to unblinded comparator drugs or concomitant medications/drug delivery systems are reported directly to the manufacturers of those drugs/devices in accordance with the package insert.

The telephone and facsimile number of the sponsor's contact persons, specific to the study, are listed in the investigator folder provided to each site. The original copy of the SAE Report Form and the fax confirmation sheet must be kept with the CRF documentation at the study site.

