8.8.3. Hepatic Function Abnormalities (Hepatotoxicity)

Increased transaminases have been reported during treatment with anti-PD-L1 (Brahmer et al 2012). Inflammatory hepatitis has been reported in 3% to 9% of subjects treated with anti-CTLA-4 monoclonal antibodies (eg, ipilimumab). The clinical manifestations of ipilimumab-treated subjects included general weakness, fatigue, nausea and/or mild fever, and increased liver chemistry tests such as AST, ALT, alkaline phosphatase, and/or total bilirubin. Hepatic function abnormality is defined as any increase in ALT or AST to $> 3 \times$ ULN and concurrent increase in bilirubin to $> 2 \times$ ULN (ie, Hy's law cases). Concurrent findings are those that derive from a single blood draw or from separate blood draws taken within 8 days of each other. Follow-up investigations and inquiries will be initiated promptly by the investigational site to determine whether the findings are reproducible and/or whether there is objective evidence that clearly supports causation by a disease (eg, cholelithiasis and bile duct obstruction with distended gallbladder) or an agent other than the investigational product. If the underlying diagnosis for the hepatic function abnormality is known (including progression of pre-existing disease such as primary or metastatic malignancy), the diagnosis should be recorded as an AE/SAE. If the underlying diagnosis for the hepatic function abnormality remains unknown, the term "hepatic function abnormal" should be used to report the AE/SAE. Hepatic function abnormality of unknown etiology, or which is considered attributable to investigational product, is required to be reported as "hepatic function abnormal" within 24 hours of knowledge of the event to the sponsor using the SAE Report Form, even if the event is considered to be nonserious.

The investigator will review the data with the medical monitor. The investigator should then use clinical judgment to establish the cause based on local standard of care and follow the subject by conducting testing as clinically indicated.

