## APPENDIX B. LABORATORY GRADING

Laboratory	Grade 1	Grade 2	Grade 3	Grade 4
Haptoglobin decreased	< LLN	–	–	–
Hemoglobin decreased	< LLN - 100 g/L	< 100 – 80 g/L	< 80 g/L	–
Hemoglobin increased	Increase in > 0 – 2 g/dL above ULN or above baseline if baseline is above ULN	Increase in > 2 – 4 g/dL above ULN or above baseline if baseline is above ULN	Increase in > 4 g/dL above ULN or above baseline if baseline is above ULN	–
Lymphocyte count decreased	< LLN – $0.8 \times 10^9$ /L	< $0.8 - 0.5 \times 10^9$ /L	< $0.5 - 0.2 \times 10^9$ /L	< $0.2 \times 10^9$ /L
Lymphocyte count increased	-	> $4000/\text{mm}^3 - 20,000/\text{mm}^3$	> $20,000/\text{mm}^3$	–
Neutrophil count decreased	< LLN – $1.5 \times 10^9$ /L	< $1.5 - 1.0 \times 10^9$ /L	< $1.0 - 0.5 \times 10^9$ /L	< $0.5 \times 10^9$ /L
Platelet count decreased	< LLN - $75.0 \times 10^9$ /L	< $75.0 - 50.0 \times 10^9$ /L	< $50.0 - 25.0 \times 10^9$ /L	< $25.0 \times 10^9$ /L
White blood cell decreased	< LLN – $3.0 \times 10^9$ /L	< $3.0 - 2.0 \times 10^9$ /L	< $2.0 - 1.0 \times 10^9$ /L	< $1.0 \times 10^9$ /L
Activated partial thromboplastin time prolonged	> ULN – $1.5 \times$ ULN	> $1.5 - 2.5 \times$ ULN	> $2.5 \times$ ULN	–
INR increased	> 1 - $1.5 \times$ ULN	> $1.5 - 2.5 \times$ ULN	> $2.5 \times$ ULN;	–
Alanine aminotransferase increased	> ULN – $3.0 \times$ ULN	> $3.0 - 5.0 \times$ ULN	> $5.0 - 20.0 \times$ ULN	> $20.0 \times$ ULN
Alkaline phosphatase increased	> ULN – $2.5 \times$ ULN	> $2.5 - 5.0 \times$ ULN	> $5.0 - 20.0 \times$ ULN	> $20.0 \times$ ULN
Aspartate aminotransferase increased	> ULN – $3.0 \times$ ULN	> $3.0 - 5.0 \times$ ULN	> $5.0 - 20.0 \times$ ULN	> $20.0 \times$ ULN
Blood bilirubin increased	> ULN - $1.5 \times$ ULN	> $1.5 - 3.0 \times$ ULN	> $3.0 - 10.0 \times$ ULN	> $10.0 \times$ ULN
CD4 lymphocytes decreased	< LLN - $0.5 \times 10^9$ /L	< $0.5 - 0.2 \times 10^9$ /L	< $0.2 - 0.05 \times 10^9$ /L	< $0.05 \times 10^9$ /L
Cholesterol high	> ULN - 7.75 mmol/L	> 7.75 - 10.34 mmol/L	> 10.34 - 12.92 mmol/L	> 12.92 mmol/L
CPK increased	> ULN - $2.5 \times$ ULN	> $2.5 \times$ ULN - $5 \times$ ULN	> $5 \times$ ULN - $10 \times$ ULN	> $10 \times$ ULN
Creatinine increased	> 1 - $1.5 \times$ baseline; >ULN - $1.5 \times$ ULN	> $1.5 - 3.0 \times$ baseline; > $1.5 - 3.0 \times$ ULN	> 3.0 baseline; > $3.0 - 6.0 \times$ ULN	> $6.0 \times$ ULN

Laboratory	Grade 1	Grade 2	Grade 3	Grade 4

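### Table 12 prints the Hy's-law permanent stop only in its Grade 3 row, so some Hy's-law cases match a Grade 2 row that says hold and then resume (minor)

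*Protocol*

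**What the plan says.** Protocol Section 5.6.3.3, Table 12, sets hepatitis management by grade.

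- **Grade 2 row** (AST/ALT or total bilirubin): withhold both drugs. Once values are back to Grade 1 or baseline, "resume study treatment after completion of steroid taper", with epacadostat one dose level lower and durvalumab unchanged. The only route to a higher row is "If toxicity worsens, then treat as Grade 3 or Grade 4". Hy's law is not mentioned.
- **Grade 3 row** (AST/ALT above 5 and below 8 × ULN, or Grade 3 bilirubin up to 5 × ULN): the last item of the restart cell reads "Permanently discontinue study treatment for any case meeting Hy's law criteria". It then gives the criteria: AST and/or ALT above 3 × ULN plus bilirubin above 2 × ULN, no initial cholestasis, no alternative cause.
- **Top row** (AST/ALT above 8 × ULN or bilirubin above 5 × ULN): discontinue both drugs.

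Section 8.2.2 uses the same Hy's-law definition and adds a reporting duty: "All occurrences of potential DILIs, meeting the defined criteria, must be reported as SAEs". Sections 8.3.2.1 and 8.8.3 also deal with reporting and review, not discontinuation. Section 5.7.1 (Withdrawal Criteria) does not name Hy's law. It makes unacceptable toxicity under Section 5.6 a mandatory withdrawal reason, and so leads back to Table 12.

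**The concern.** The table is read by row. Someone with a Grade 2 laboratory result goes to the Grade 2 row and finds an instruction to hold and later resume. The Hy's-law stop sits one row down, in a cell that appears to concern Grade 3 values only. If some Hy's-law cases are Grade 2 on both tests, the row they match gives the opposite action from the one the protocol intends. A site following that row alone would plan to re-dose a subject who should come off treatment permanently.

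**Working it through.** **1. Do Hy's-law cases with only Grade 2 values exist?** Grade limits are from SAP Appendix B (bilirubin under "Blood bilirubin increased"); Hy's-law limits are from Table 12 and Section 8.2.2.

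| Test (× ULN) | Hy's law | Grade 2 | Overlap |
|---|---|---|---|
| AST/ALT | > 3 | > 3.0 to 5.0 | > 3 to 5 |
| Bilirubin | > 2 | > 1.5 to 3.0 | > 2 to 3 |

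The overlap is not empty. Example: ALT 4 × ULN and bilirubin 2.5 × ULN, normal alkaline phosphatase, no other cause. This meets Hy's law and is Grade 2 on both tests. The Grade 3 row needs AST/ALT above 5 × ULN or Grade 3 bilirubin, so the case matches the Grade 2 row. If either value is higher, the case reaches the Grade 3 row, where the stop is printed, or the discontinue row.

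**2. Is the stop stated independently elsewhere?** No. Sections 8.2.2, 8.3.2.1 and 8.8.3 require reporting or review, and Section 5.7.1 reaches the stop only through Section 5.6.

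**3. Which Grade 2 Hy's-law cases could resume without approval under the 4-week rule?** The Grade 2 row starts steroids if the event persists beyond 3–5 days and tapers them over at least 28 days before resumption. The shortest such hold is:

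- 3 + 28 = 31 days, to
- 5 + 28 = 33 days.

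Both exceed 4 × 7 = 28 days. If steroids start earlier because the event worsens, the taper alone still takes at least 28 days. So completed steroid courses reach the provision in Section 5.7.1 that begins "Investigators who wish to continue treatment after a treatment delay of 4 weeks should consult" and requires medical-monitor approval. What is left is mainly a hold that ends quickly without steroids.

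**4. What still applies to a brief, steroid-free hold?**

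- Section 5.6.2: any interruption for liver-test abnormalities is discussed with the medical monitor before restart.
- Section 5.6.3: irAEs of Grade 2 or higher are discussed with the monitor at once.
- Section 8.3.2: the SAE "must be reported to the sponsor (or designee) within 24 hours of learning of its occurrence".
- Section 8.8.3: "The investigator will review the data with the medical monitor".

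Each is a report or a discussion. None is itself a stop.

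**5. How often?** The Amendment 5 rationale in Appendix E reports no drug-induced liver injury during dose escalation. It does not give the number treated. Assuming between 18 (6 cohorts × the minimum of 3) and 36 (the planned maximum), zero events gives a one-sided 95% upper limit of 1 − 0.05^(1/n):

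- n = 36: about 8%
- n = 18: about 15%

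These limits cover all drug-induced liver injury, of which the Grade 2 window is a part. The event looks uncommon, but the data do not rule it out.

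**The case against.** The best reply is that the stop says 'any case' and carries its own thresholds, with an AST/ALT limit (3 × ULN) below the entry value of the row it sits in (5 × ULN). It is also the only text in Table 12 that addresses transaminases and bilirubin rising together. A specific rule for any case should override a general restart rule. A site must recognise Hy's law to report the SAE, and both site and monitor would then have to miss a sentence naming Hy's law in the same table. This stands as to intent and as to the low risk. It does not cure the placement, because the Grade 2 row gives an unqualified resume instruction and nothing in that row points to the exception.

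A reader might also infer that the protocol follows a fixed convention of repeating a cross-grade stop in every row it governs, so that Table 12 deliberately limits this one to Grade 3. The documents do not support that. In Table 13 the stop for Stevens-Johnson syndrome and toxic epidermal necrolysis appears only in the Grade 3 row, with bullous rash covered in the lead-in text. In Table 17 the pancreatitis stop is absent from the Grade 2 row. Only Table 18, with its 'Any' row for biopsy-proven myocarditis, is a close parallel, and it is useful as a model for the fix.

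**Conclusion.** The conflict is real and minor. For AST/ALT above 3 to 5 × ULN with bilirubin above 2 to 3 × ULN, the Grade 2 row gives the wrong action for a case in which the protocol intends a permanent stop. Practical exposure is mainly brief, steroid-free holds, with monitor discussion and SAE reporting still in place. No endpoint, estimate or analysis changes.

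A reader might go further and infer that the protocol has no Hy's-law stopping rule, or that it means Grade 2 Hy's-law cases to be re-dosed. Neither follows: the rule exists, its thresholds match Section 8.2.2, and its wording covers every case. Nor does the silence of Section 5.7.1 show an omission, since its reference to Section 5.6 can be read to bring the stop in.

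The conclusion assumes that sites grade as in SAP Appendix B. The SAP uses CTCAE v4.03 and the protocol v4.0. Table 12's own Grade 3 AST/ALT floor of 5 × ULN agrees with the SAP limits.

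**What to change.** Move the Hy's-law permanent stop to an 'Any grade' row at the top of Table 12, following Table 18, or state it in the text that introduces the table in Section 5.6.3.3. In the Grade 2 row, add to the resume instruction: 'except cases meeting Section 8.2.2'. Cite 8.2.2 rather than 8.8.3, because 8.8.3 applies the Hy's-law label without the cholestasis and alternative-cause conditions. A matching bullet in Section 5.7.1 is optional, since it largely repeats the existing reference to Section 5.6.

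The cost is wording only: no tests, visits or analyses are added. Subjects with Grade 2 values who meet Hy's law lose a route to resumption that the existing 'any case' sentence already means to close.
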